7.1 Secondary Endpoints

Secondary endpoints include:

1. Viral load measured in nasopharyngeal swab by Cycle Threshold at 0, 24, 48, and 72 hours after initiation of core warming
2. Duration of mechanical ventilation
3. Patient mortality

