More recently, simulations of the receptor binding domain (RBD) of SARS-CoV-2 found that it is more flexible than SARS CoV, especially near the binding site, suggesting that the RBD will have a higher entropy penalty upon binding angiotensin-converting enzyme II (ACE2) compared to the RBD of SARS-CoV.[33] Consequently, SARS-CoV-2 may be more temperature-sensitive in terms of human infection than SARS-CoV.[33]

Hyperthermia induced by directly heating the body (as opposed to fever induced by introducing bacterial extracts or other foreign substances) is normally limited to 41.8 to 42°C when used to kill tumor cells in cancer treatment, with minimal adverse effects.[34-37] Furthermore, hyperthermia and elevated temperature have been found to have positive impacts on the immune system. Cells have been found to exhibit increased levels of heat-shock proteins, specifically HSP70 [38] and HSP90, [39] which are directly related to and/or cause antigen presentation and cross-presentation, activation of macrophages and lymphocytes, and activation and maturation of dendritic cells,[40] all of which are essential antiviral immune responses. Notably, fever has often abated by the time a COVID-19 patient requires mechanical ventilation.[41]

The aim of this study is to determine the effect of active core warming patients diagnosed with COVID-19 and undergoing mechanical ventilation. We hypothesize that active core warming will reduce the severity of acute respiratory distress syndrome, reduce the duration of mechanical ventilation, and improve survival compared to standard of care.

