2.2 Secondary Objectives

1. Determine the change in viral load measured in nasopharyngeal swab by Cycle Threshold at 0, 24, 48, and 72 hours after implementation of core warming of ventilated patients, and compare this change to patients undergoing standard care.
2. Measure the impact of core warming on duration of mechanical ventilation.
3. Determine impact of core warming on patient mortality.

3 Investigational Plan

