3.1.3 Follow Up (Day 30)

Follow up data will be collected at 30 days following initiation of study treatment.

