4.4 Duration of Study Participation

Participants will be involved for approximately 30 days, including screening, treatment, and follow-up. After consent, patient participation in the intervention phase will last 72 hours for active treatment. The follow up for determination of outcome and duration of mechanical ventilation will occur at 1-month post-treatment. Additional data will be collected via chart review.

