7.2 Sample Size and Power Determination

Based on a prior study in patients with sepsis, a maximum temperature of 38.3°C to 39.4°C was associated with survival (aHR 0.61 [95% CI, 0.39-0.99]).[29] However, the effect of warming specific to COVID-19 patients remains uncertain, and as such, we are unable to accurately perform a power calculation for this pilot study. We believe that a total of 10 patients for each group will be required to yield the necessary pilot data to make an appropriate conclusion regarding the potential utility of core warming in reducing viral shedding, improving pulmonary physiology, reducing mechanical ventilation duration, and increasing patient survival. It is anticipated that data from this pilot study can be used for planning future larger studies.

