7.3 Statistical Methods

We will utilize standard measures to report outcomes and measure differences between groups. Specifically, we will use descriptive statistics, including mean (standard deviation) and median (interquartile range). Normality will be assessed using histograms and the Kolmogorov–Smirnov test. Categorical variables will be compared using the chi-squared test or Fisher exact test. Continuous variables will be compared using the independent samples t or Mann–Whitney U test.

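### Duration of mechanical ventilation is compared with no rule for patients who die on the ventilator, and neither plausible reading of the plan gives an interpretable comparison

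*Combined protocol and SAP*

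**What the plan says.** Section 2.2 sets the objective: "Measure the impact of core warming on duration of mechanical ventilation". The Study Summary carries the same objective, and sections 3.2.2 and 7.1 list "Duration of mechanical ventilation" as a secondary endpoint. Mortality is a separate item, not combined with it.

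The only analysis rule is the general one in 7.3: "Continuous variables will be compared using the independent samples t or Mann–Whitney U test". No start, end or unit is given for the duration. There is no rule for death on the ventilator, for re-intubation, or for a patient still ventilated at follow-up. No time-to-event, competing-risk or ventilator-free-days measure appears anywhere.

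The nearest text to a death rule is 7.4, which analyses patients who were enrolled, randomized and completed the study. Section 6.5 says that completion will be documented for each subject. Neither says whether a patient who dies has completed.

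The follow-up window has three descriptions. Section 3.1.3 says "Follow up data will be collected at 30 days following initiation of study treatment"; 4.4 says "The follow up for determination of outcome and duration of mechanical ventilation will occur at 1-month post-treatment"; 6.2.3 counts 30 days from study completion.

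**The concern.** The patients are ventilated and mortality is itself an endpoint, so deaths on the ventilator must be expected. Section 1.2 hypothesizes that warming will "reduce the duration of mechanical ventilation, and improve survival compared to standard of care". If death ends the duration, those two benefits can pull the same number in opposite directions: faster extubation shortens it, and averting an early death lengthens it. An arm that loses patients early can look as if it weans faster.

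Section 7.2 wants the pilot to support a conclusion on the potential utility of warming in "reducing mechanical ventilation duration, and increasing patient survival", and to inform larger studies. A duration estimate that mixes death with extubation serves neither purpose. The study team is unblinded (5.2, 8.6), so the scoring rule should be fixed before the data are seen.

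**Working it through.** **The plan's own figure.** There is none to reproduce. Section 7.2 declines a power calculation and gives no mortality rate, extubation rate or ventilation time. Everything below is illustration under stated assumptions.

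**Step 1: a worked case, 11 per arm (3.1).** Assume survivors are weaned at day 14 in both arms, with 5 control deaths and 3 warmed deaths.
- Deaths at day 5, counted to death: control (5×5 + 6×14)/11 = 9.9 days; warmed (3×5 + 8×14)/11 = 11.5 days. Warming looks 1.6 days worse after saving two patients.
- Deaths at day 18 instead: control (5×18 + 6×14)/11 = 15.8; warmed (3×18 + 8×14)/11 = 15.1. The sign reverses.
- Survivors only: 14 vs 14, undistorted because the added survivors wean like the rest. If the two saved patients were weaned at day 18, the warmed mean would be (6×14 + 2×18)/8 = 15.0 vs 14.0.
- Ventilator-free days (VFD) to day 30, death = 0: 6×16/11 = 8.7 vs 8×16/11 = 11.6, whichever day the deaths occur.

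**Step 2: competing hazards.** Assume constant daily hazards of extubation (he) and death (hd), a 30-day cap and no death after extubation. With l = he + hd and q = 1 − exp(−30l):
- mean duration = q/l
- ventilator deaths = hd·q/l
- VFD = he·(30/l − q/l²)

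| Scenario | he | hd | l | q | Mean duration (days) | Ventilator deaths | VFD |
|---|---|---|---|---|---|---|---|
| Control | 0.06 | 0.04 | 0.10 | 0.950 | 9.5 | 38% | 12.3 |
| Death hazard doubled | 0.06 | 0.08 | 0.14 | 0.985 | 7.0 | 56% | 9.8 |
| Death hazard ×0.61 | 0.06 | 0.0244 | 0.0844 | 0.921 | 10.9 | 27% | 13.6 |
| ×0.61 and extubation +26% | 0.0756 | 0.0244 | 0.10 | 0.950 | 9.5 | 23% | 15.5 |

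The 0.61 is the adjusted hazard ratio that 7.2 cites from a sepsis cohort, borrowed here as an effect size only. Over its interval of 0.39 to 0.99, mean duration runs from 11.9 down to 9.5 days.

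The 26% in the last row was solved for, not predicted: he = 0.10 − 0.0244 = 0.0756, and 0.0756/0.06 = 1.26. It is the extubation gain that exactly cancels the survival gain. In general that gain is 0.39·hd/he, which runs from 0.39×0.02/0.10 = 8% to 0.39×0.04/0.03 = 52% over he 0.03–0.10 and hd 0.02–0.04.

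**Step 3: what a trial of this size would show** (40,000 simulated trials, 11 per arm).
- Death hazard doubled: the harmed arm has the shorter mean in about 78% of trials, and significantly so in about 10% (t) or 9% (Mann–Whitney). With no effect the figures are 50% and about 2.4%.
- Death hazard ×1.25: shorter in about 58%, significantly in 3% to 4%.
- Both benefits, at the cancelling value: the warmed arm is shorter in 50% of trials, while its mean VFD is higher in about 74%.

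**Step 4: dependence on timing.** Now fix each patient's fate independently of extubation time, with survivors' extubation hazard 0.10, and raise the death share from 38% to 56%. Count-to-death duration goes from 8.4 to 7.9 days if deaths come early (death-time hazard 0.15), stays at 9.5 if the timing matches (0.10), and goes from 11.2 to 12.0 if deaths come late (0.06). Survivors-only duration stays at 9.5. VFD falls from 12.7 to 9.0 in all three.

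**Step 5: the window.** Counting from the end of a 72-hour intervention rather than its start gives 33 days. Control duration barely moves (9.50 to 9.63 days), but control VFD goes from 12.3 to 14.0.

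**The case against.** **Mortality is already reported beside duration.** This stands in part. Under doubled death hazard, more deaths appear in the harmed arm in about 75% of trials, and deaths point the wrong way in only 13% to 14%, against about 31% for mean VFD. Under ×0.61 alone, deaths are fewer in about 64% of trials while VFD is higher in about 60%. What mortality cannot do is isolate a change in extubation rate that raw duration hides.

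**Every hazard is assumed, and the sign can go either way.** This also stands. A reader might infer that the plan is biased against warming, or that a survival gain must look like slower weaning. The documents give no death timing, so they do not support that; Steps 1 and 4 show the reversal. What is secure is that the number has no fixed meaning without a death rule.

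**Section 7.4 may already exclude deaths.** A reader might infer a survivors-only rule from it. The text does not say so, because completion is undefined. Under that reading the count-to-death distortion does not arise, but the comparison is no longer between the randomized groups.

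**Duration and deaths can disagree by chance.** Under doubled hazard the harmed arm is shorter with no more deaths in about 19% of trials, and with fewer deaths in about 10%. A reader might take this as harm being masked. With no effect the same patterns occur in about 28% and 19%, so they reflect noise at 11 per arm.

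**VFD goes further than one sentence about deaths.** It does replace a stated objective with a composite. One sentence would remove the ambiguity, but counting to death or dropping deaths would still leave an unsound comparison.

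**Conclusion.** The omission is real and should be fixed. As written, the duration comparison has two plausible readings: one scores death like extubation on the same day, and the other abandons the randomized groups. Under the assumed hazards, the first reading shifts the mean by 2.5 days (9.5 vs 7.0) when the death hazard doubles and by 1.4 days (9.5 vs 10.9) when it falls by 39%. It can also hide a real extubation gain completely, although the 26% used to show this is the cancelling value and not an expected effect. Sizes and direction rest on constant hazards and on deaths occurring earlier than extubation would have; later deaths reverse the direction.

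The weight is moderate. This is a secondary endpoint in a 22-patient pilot with no decision rule attached, and false significance reaches only about 9% to 10% even under doubled hazard. The loss is an interpretable estimate and usable planning data.

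**What to change.** - In the Study Summary, 2.2, 3.2.2 and 7.1, make the compared endpoint ventilator-free days from randomization to day 30: days alive and off mechanical ventilation, 0 for death by day 30, with days after re-intubation counted as ventilated. Compare it by the Mann–Whitney test already named, in all randomized patients as assigned. A competing-risk analysis of extubation, with death as the competing event, is an acceptable alternative.
- In 7.4, state that patients who die are included. Report unknown day-30 status by arm.
- Report duration in survivors and deaths by arm beside the endpoint, descriptively, and interpret them jointly.
- Use one day-30 origin that exists in both arms, such as randomization, and reconcile 3.1.3, 4.4 and 6.2.3. The discrepancy causes no between-arm bias, but VFD needs the window fixed.

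The cost is wording plus case report form fields for extubation, re-intubation and death dates. The section 6 schedule records ventilator settings only through Day 1–2, but 4.4 allows chart review.

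The downside is that VFD is a composite. It does not isolate ventilation time and it scores death the same as being alive but ventilated at day 30. At 22 patients it still favours the harmed arm in about 31% of trials under doubled death hazard, and under both benefits at the cancelling value it reaches significance in only about 8%.

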7.2 Sample Size and Power Determination

Based on a prior study in patients with sepsis, a maximum temperature of 38.3°C to 39.4°C was associated with survival (aHR 0.61 [95% CI, 0.39-0.99]).[29] However, the effect of warming specific to COVID-19 patients remains uncertain, and as such, we are unable to accurately perform a power calculation for this pilot study. We believe that a total of 10 patients for each group will be required to yield the necessary pilot data to make an appropriate conclusion regarding the potential utility of core warming in reducing viral shedding, improving pulmonary physiology, reducing mechanical ventilation duration, and increasing patient survival. It is anticipated that data from this pilot study can be used for planning future larger studies.

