Objectives	
Primary:
 
 • Determine the change in PaO₂/FiO₂ ratio at 0, 24, 48, and 72 hours after implementation of core warming of ventilated patients, and compare this change to patients undergoing standard care. 
Secondary:
 
 • Determine the change in viral load measured in nasopharyngeal swab by Cycle Threshold at 0, 24, 48, and 72 hours after implementation of core warming of ventilated patients, and compare this change to patients undergoing standard care. • Measure the impact of core warming on duration of mechanical ventilation. • Determine impact of core warming on patient mortality.
Number of Participants	22
Length of Participation	72 hour intervention phase; 30 day follow up

Inclusion Criteria	
 1. Patients above the age of 18 years old. 2. Patients with the diagnosis of COVID-19 requiring mechanical ventilation. 3. Patient maximum baseline temperature (within previous 12 hours) < 38.3°C. 4. Patients must have surrogate or legally authorized representative able to understand and critically review the informed consent form.
Exclusion Criteria	
 1. Patients without surrogate or legally authorized representative able to provide informed consent. 2. Patients with contraindication to core warming using an esophageal core warming device. 3. Patients known to be pregnant. 4. Patients with <40 kg of body mass. 5. Patients with DNR status. 6. Patients with acute stroke, post-cardiac arrest, or multiple sclerosis.
Investigational Device	Attune Medical esophageal heat transfer device – ensoETM. Used as indicated for patient temperature management.
Duration of administration	72 hours
Reference therapy	Standard temperature management as routine at study site
Statistical Methodology	A total of 11 patients for each group will be required to yield the necessary pilot data regarding the feasibility and effect of core warming on viral load and ventilation requirements.
Safety Evaluations	Standard adverse event monitoring (device is in widespread use for patient warming and cooling).
Data and Safety Monitoring Plan	The PI and research team will be responsible for data and safety monitoring.

This study will be conducted in full accordance with all applicable study site research policies and procedures and all applicable federal and state laws and regulations.

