3.1 General Design

This is a small scale pilot study to evaluate if core warming improves respiratory physiology of mechanically ventilated patients with COVID-19, allowing earlier weaning from ventilation, and greater overall survival. This prospective, randomized study will include 22 patients diagnosed with COVID-19, and undergoing mechanical ventilation for the treatment of respiratory failure. Patients will be randomized in a 1:1 fashion with 11 patients (Group A) randomized to undergo core warming, and the other 11 patients (Group B) serving as the control group who will not have the ensoETM device used. Patients randomized to Group A will have core warming initiated in the ICU or other clinical environment in which they are being treated after enrollment and provision of informed consent from appropriate surrogate or legally authorized representative.

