4.5 Total Number of Subjects and Sites

Recruitment will end when 22 participants are randomized.

5 Study Intervention

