7.3.2 Interim Safety Analysis

All subjects entered into the study and randomized at the baseline timepoint will have detailed information collected on adverse events for the overall study safety analysis. An interim safety analysis will be performed after the first 10 subjects are enrolled in the trial. At this time the safety and tolerability of the study device will be assessed and if deemed safe and appropriate, enrollment will continue to 22 subjects.

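### Section 7.2 justifies the trial on 10 patients per group, but the rest of the protocol plans 11 per group (22 in total), and nothing reconciles the two figures

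*Combined protocol and SAP*

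**What the plan says.** Section 7.2 (Sample Size and Power Determination) explains that the effect of warming in COVID-19 is too uncertain for a power calculation and then gives a number by judgement: "We believe that a total of 10 patients for each group will be required".

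The Statistical Methodology row of the Study Summary makes the same kind of statement with a different number: "A total of 11 patients for each group will be required to yield the necessary pilot data". The participant count in that table is 22.

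The remaining sections agree with the Study Summary:

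- Section 3.1: "This prospective, randomized study will include 22 patients diagnosed with COVID-19", and "Patients will be randomized in a 1:1 fashion with 11 patients (Group A) randomized to undergo core warming", with the other 11 as controls.
- Section 4.5: "Recruitment will end when 22 participants are randomized". This gives the total only.
- Section 7.3.2: after a satisfactory interim safety review, "enrollment will continue to 22 subjects".
- Section 8.7: a further data review is set for when 22 patients have been enrolled.

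**The concern.** The sample size is a figure that the trial relies on, and readers look for its justification in section 7.2. That section supports 10 per group; the trial is set up for 11. Because there is no power calculation, the number in 7.2 is the whole of the justification, and no formula can be rerun to show which figure was meant.

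What is at stake is traceability. A later report that cites 7.2 for the planned size would give 20, and one that cites 3.1 or 4.5 would give 22. If 10 was meant as the number of patients needed for analysis, the plan contains an attrition assumption that it never states. That would matter because section 7.4 limits the analysis to patients who completed the study and section 6.5 allows withdrawal.

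**Working it through.** **1. Totals under 1:1 allocation (ratio from section 3.1).**

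| Source | Per group | Total |
|---|---|---|
| Section 7.2 | 10 | 2 × 10 = 20 (implied) |
| Study Summary | 11 | 22 (stated; 2 × 11) |
| Section 3.1 | 11 | 22 (stated) |
| Section 4.5 | 22 / 2 = 11 (implied) | 22 (stated) |
| Section 7.3.2 | 22 / 2 = 11 (implied) | 22 (stated) |
| Section 8.7 | 22 / 2 = 11 (implied) | 22 (stated) |

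The gap is 1 per group and 2 in total. A total of 20 appears nowhere.

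**2. Can either figure be reproduced?** No. Section 7.2 gives no alpha, power, SD or target difference. The one effect it cites, an adjusted hazard ratio of 0.61 for survival, is not the source of the number. Assuming two-sided alpha 0.05 and 80% power (neither is in the documents), Schoenfeld's formula gives

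events = 4 × (1.960 + 0.842)² / (ln 0.61)² ≈ 129,

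which is far above 20 or 22 patients.

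**3. Could a dropout allowance link 10 to 11?** With N randomised = n evaluable / (1 − d), 11 per group covers 10 evaluable when d ≤ 1 − 10/11 = 9.1%, that is, one loss per arm. At d = 9%, 10 / 0.91 = 10.99, rounded up to 11. At d = 10%, 10 / 0.90 = 11.1, rounded up to 12. An allowance of up to about 9% would therefore work arithmetically. Sections 4.5, 6.5, 7.2 and 7.4 state no loss rate, inflation or replacement of withdrawn patients.

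**4. Could the interim look explain the 10?** No. Sections 7.3.2 and 8.7 place a review after 10 patients in the whole trial, not 10 per group.

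**5. Statistical size of the gap.** The half-width of a 95% t interval for a difference in means, in units of the common SD, is t(0.975, 2n − 2) × √(2/n):

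- n = 10: 2.101 × √(2/10) = 2.101 × 0.4472 = 0.94 SD
- n = 11: 2.086 × √(2/11) = 2.086 × 0.4264 = 0.89 SD

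This assumes equal variances and that every randomised patient contributes data.

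**The case against.** The strongest reply is that the mismatch has almost no practical consequence. Section 4.5 contains the recruitment rule, it says 22, and sections 3.1, 7.3.2 and 8.7 and the participant count in the Study Summary agree. Section 7.2 declines a power calculation, so no planned power or precision claim rests on the 10. Nothing is miscalculated; most likely one number was not updated. All of this stands, and it is why the point is minor.

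A reader might infer more from the contradiction than the documents support:

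- *That recruitment could properly stop at 20.* Section 7.2 contains no recruitment rule, and no section allows stopping at 20.
- *That the precision of the reported results depends on which figure is taken.* Precision will depend on the patients actually analysed, and the plan makes no precision statement that would change.

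It might also be argued that the two statements describe different requirements, since they list somewhat different aims. The Study Summary mentions feasibility and the effect on viral load and ventilation requirements; 7.2 lists viral shedding, lung physiology, ventilation time and survival. But each offers a per-group number as what the pilot needs, and neither list gives a reason for the numbers to differ.

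The evaluable-versus-randomised reading is possible arithmetically, but the text does not support it: the Study Summary presents 11 as the number required, not as 10 plus a margin.

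**Conclusion.** The point holds as a minor internal inconsistency, wrong as written. Section 7.2 requires 10 per group (20), every other statement of the sample size gives or implies 11 per group (22), and nothing reconciles them. The intended size is not in doubt; the written rationale does not match it.

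The gap is 2 patients. Its effect on precision is about 0.05 SD in the 95% half-width (0.94 against 0.89 SD). Those half-widths are a best case, because section 7.4 analyses completers only. The contradiction itself rests on no assumption and can be seen by comparing the sections.

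**What to change.** Amend the one sentence in section 7.2 in one of two ways:

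1. Change the figure to 11 per group, 22 randomised, so that it agrees with the Study Summary and sections 3.1, 4.5, 7.3.2 and 8.7.
2. If 10 per group is meant as the number with analysable data, say so, keep 11 per group as the number randomised, and state the loss assumed. That loss can be at most about 9%, or one patient per arm. The Study Summary sentence should then carry the same distinction.

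The first is the simpler and fits the rest of the protocol. Either is an edit to the text, with no extra patients and no change to the design, schedule or analysis.
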